### **3.1.2 Parametric subgroup analysis – decomposing the within and across site effects**

We assume that absolute rates (risks) of second vaccine will not lie at the ends of the interval [0,1]. If that is the case, then we can estimate risk differences with subgroups and then across subgroups in the following 3-step process.

**Step 1:** Using a generalized linear effects, create a site-level variable that equals the mean rate of the group at the site. If at one site, for example, 20% of the children have a chronic medical condition, then create a factor =0.2 for that site (called group\_bar).

**Step 2:** Specify a generalized linear model with the following covariates where treatment and group are 0/1 factors:

Treatment + group + treatment\*group + group\_bar + treatment\*group\_bar + covariates.

This model will decompose the within-site effect of treatment by group and the across-site effect of treatment by group.

### **3.2 Subgroup analysis – time-to-event – secondary**

The goal is to identify subgroups of patients who responded well (or not at all) to the intervention in terms accelerating the time to completing of the vaccination series. Contrasts between groups will be estimated and reported as

Restricted mean survival time analyses can be done with interactions (treatment\*subgroup).

Effect modification will be estimated on the difference scale.

Using pseudo-observation approach:

Stata: `glm pseudo treat##subgroup, vce(cluster site)`

Results can be standardized for covariates (see above).

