#### **2.3.1 Time zero**

Time zero for all time to event analyses is the date of child's initial vaccine dose.

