### 2.3.4 Risk difference (of completion of vaccine series) as of a given time

The purpose of this analysis is to re-express the results of Kaplan Meier survival estimates to generate more interpretable results. It is therefore an alternative method to express the results and will not be considered as a multiple test in need of adjusting confidence intervals. This analysis is not separate from the Kaplan Meier analysis. Rather it only quantifies the values of the two curves (y) at a given value of time (e.g. 42 days). This is therefore, just a re-expression of the Kaplan Meier plot.

Use of pseudo-observation approach with syntax:

```
Stpsurv, at(time1) failure after(time0),
```

Where time(1) can be as of day 42, 60, and 90.

As April 30 does not account for different days of follow up per child, it will not be possible to use that date for analysis. Programming details appear in Stata program “stpm2” (Lambert, Andersson, Royston).

Syntax is (approximately):

```
standsurv, at1(treatment 0) at2(treatment 1) timevar(timevar) ci  
contrast(difference)
```

See stpm2 syntax for “standsurv”

“ci” refers to cumulative incidence

“timevar” needs to take on the value 42, 60 and 90

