### 2.3.5 Restricted mean survival curves (RMST)

RMST will not be a primary analysis, and we will not consider it to be a separate look at the data. Rather, it is another method of reporting the data, and we will not adjust confidence bounds for multiple comparisons.

We will implement restricted mean survival time analysis to compare intervention versus usual care groups (if needed, after adjusting for covariates that are not balanced

between groups) and to arrive at meaningful estimates that do not require proportional hazards assumptions.

We have moved beyond hazard ratios because of the assumptions underlying Cox models and the shortcoming of interpretations (Hernan 2010). If we set a truncation time (Day 42), then RMST has the interpretation "if we follow children for 42 days, they will receive the second vaccine on average by day X" (Royston 2011, 2013). Estimation of between group differences are also possible. The more theoretical interpretation is the area under the survivor function until the time of truncation.

Preiminary analysis of available time per child (analysis blinded to outcome and to the treatment assignment) showed that between 84% and 90% (depending on season) of children has observation windows that extended to day 90 from date of first dose.

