### 2.3.5.1 RMST

*Stata: strmst2:*

RMST and curves are estimable using strmst2 (Cronin 2016) in Stata

Will perform conventional RMST analysis:

Requires "stset" as preliminary command.

Strmst2 treat, tau(50) (will not allow factors), where "tau" is the largest time of observation and should be the minimum (by group) of the maximum follow up time (within group).

Observation time starts at the time of the first dose of vaccine and ends on April 30, of the season year or when the child received the second does, whichever was earlier.

For this study, we pre-specify several values of tau:

- (i) 42 – the number of days within which children should receive the second dose
- (ii) 60 days
- (iii) 90 days

Adjustment for covariates using strmst2pw

Robust confidence intervals.

This approach has no support for robust confidence intervals (or for strata). For that reason, we will check all confidence bounds by using bootstrap percentile methods, with 999 resamples at the site level (code will be developed for Stata).

Note: Alternative RMST code available from Royston (2015) using Stata's code strmst. This will be a backup in the event that Cronin's code fails.

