##### **3.0.1.1 Available for all children**

- child age-group (6-23 months; 2-8 years)
- child gender (male; female)
- child health insurance (public/uninsured; commercial (including Tricare)). This variable is used as a partial indicator of socioeconomic status.
- seasonality of the initial dose (early influenza season, mid-season, late season)

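### The time-to-event subgroup model in SAP section 3.2 can bias effect modification by season of first dose, because first-dose date sets each child's censoring time

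*Combined protocol and SAP*

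**What the plan says.** SAP section 3.2 proposes restricted mean survival time (RMST) analyses with treatment-by-subgroup interactions, fitted by a pseudo-observation regression: "glm pseudo treat##subgroup, vce(cluster site". It adds that "Effect modification will be estimated on the difference scale".

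Section 2.3.4 gives the only syntax for generating pseudo-observations, "Stpsurv, at(time1) failure after(time0", with no by-group, stratum or weighting term. On horizons it says "Where time(1) can be as of day 42, 60, and 90". Section 2.3.5.1 sets RMST truncation times ("For this study, we pre-specify several values of tau") at the same three days.

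Section 3.0.1.1 lists among the candidate modifiers "seasonality of the initial dose (early influenza season, mid-season, late season", without cut dates.

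Three statements fix follow-up. Section 2.3.1: "Time zero for all time to event analyses is the date of child's initial vaccine dose". Section 2.3.5.1 ends observation at April 30 or the second dose, whichever is earlier. Section 2.1 calls dropout negligible. Section 2.3.5 reports that a preliminary analysis "showed that between 84% and 90% (depending on season) of children has observation windows that extended to day 90 from date of first dose".

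**The concern.** Regression on pseudo-observations from a single Kaplan-Meier curve is valid when censoring is independent of the covariates in the regression. Here one of those covariates is a grouping of first-dose date, and first-dose date determines how long a child can be followed. Late-season children are censored early, so from some point on the pooled curve is carried by early- and mid-season children. Late-season pseudo-values then reflect the late-season treatment contrast only for as long as late-season windows last.

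Randomization does not help: it balances follow-up between arms, not between season categories. The rule in section 2.3.5.1 for choosing the truncation time looks at follow-up by group, which in that command means treatment arm, and it stands beside fixed values of 42, 60 and 90 days. Section 2.3.4 recognises that children have unequal follow-up to April 30, but section 3.2 does not carry this into the subgroup model.

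Section 3.2 is meant to find children who responded well or not at all. A shrunken late-season estimate could suggest that reminders work less well for children who start late when they work equally well.

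**Working it through.** **1. What the documents fix.** Maximum follow-up = April 30 minus first-dose date. In 2018 and 2019 April 30 is day 120 of the year:
- a 90-day window needs a first dose by day 120 - 90 = 30, January 30;
- a 60-day window, by day 60, March 1;
- a 42-day window, by day 78, March 19.

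The plan's 84% to 90% comes from trial data and cannot be reproduced; it is used as an input. It leaves 100 - 90 = 10% to 100 - 84 = 16% with windows under 90 days, necessarily the latest first doses. The shares under 60 and 42 days are not reported.

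**2. Mechanism.** Take early/mid and late children with the same event-time distribution within each arm. Let S(t) be the pooled probability of no second dose by day t, λ(u) the pooled daily hazard, and f_a(u) and S_a(u-) the event probability on day u and the at-risk probability in arm a. The large-sample mean pseudo-value of S(t) for arm a in season category z is

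S(t) - S(t) × Σ_{u≤t} w_z(u) × [f_a(u) - S_a(u-)λ(u)] / S(u), with w_z(u) = G_z(u)/G(u),

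where G_z(u) is the share of category z with a window of at least u days and G(u) is the pooled share. Each day's arm contrast is therefore weighted by w_z(u), where unbiasedness needs 1.

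Example: 16% late, late windows uniform over 1 to 89 days.

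| Day | Late share | Pooled share | Late weight | Early/mid weight |
|---|---|---|---|---|
| 42 | 48/89 = 0.54 | 1 - 0.16 × 0.46 = 0.93 | 0.58 | 1.08 |
| 60 | 30/89 = 0.34 | 1 - 0.16 × 0.66 = 0.89 | 0.38 | 1.12 |
| 90 | 0 | 0.84 | 0 | 1.19 |

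The late effect is shrunk and the other slightly inflated. If the arms are identical, the bracket is the same in both and their difference is zero whatever the weights.

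**3. Size.** The documents give up to 4,000 parents over two seasons, 1:1 allocation, and a background second-dose rate of 40-60%. The following are assumed:
- control completion of 30/42/50% by days 42/60/90;
- a constant +8-point effect, equal in all season categories, so the true interaction is 0;
- 10% or 16% with windows under 90 days.

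Simulation with exact leave-one-out pseudo-values from one pooled curve gives this spurious late-minus-early/mid interaction, in points:

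| Late season starts | Windows under 90 days | Day 60 | Day 90 |
|---|---|---|---|
| After January 30 | uniform, 1-89 days | -3.1 to -3.4 | -3.9 to -4.1 |
| After January 30 | declining through spring | about -1.5 | -2.1 to -2.2 |
| After January 30 | all at least 42 days | -0.2 to -0.5 | -1.2 to -1.3 |
| January 1 | the three patterns | 0 to -2.4 | -0.3 to -2.9 |

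In the first row the late effect is estimated at 4.5-4.7 points at day 90, against 8.5-8.8 in early/mid. Day 42 is off by -2.9 to -3.0 points, and RMST shows a spurious 0.7-0.8 days at 60 and 1.8-1.9 days at 90. With completion interpolated linearly between the assumed points, the formula in step 2 gives -1.2 at day 90 for the third row.

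A second set-up (2,000 children, 13% late, 7-point completion gain, true day-90 late effect 6.4) gives late estimates of 2.6 (uniform), 3.9 (declining) and 5.0 (all at least 42 days).

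**4. Other effect shapes, day 90.** An effect growing 4/6/8 points by days 42/60/90 gives -1.2 to -5.6. A converging effect of 10/8/5 gives -0.9 to +1.5. A null effect shows nothing beyond simulation error (at most about 0.25 points).

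**5. False-positive rate** (first row, 16%, unclustered two-sided 5% test, no Bonferroni). At day 90, a true-zero interaction is rejected in 17% of trials of 2,000 and 24% of trials of 4,000; at day 60, in 13% and 16%. With all windows at least 42 days, or a null effect, rejection is about 5-6%.

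**6. Within-category curves.** With late season starting January 1 and a true effect of 8.0, pseudo-observations from the late category's own curve give 7.8-8.3 at day 60 and 7.7-8.3 at day 90. The pooled version gives 6.2-8.0 and 5.9-7.7.

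**The case against.** **Pooling and the cut dates are not stated.** This stands. Pooling is the natural reading of one unstratified command and one pseudo-observation variable, but it is an inference. Section 3.0.1.1 gives three categories and no dates, so a reader may not equate late season with first doses after January 30.

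**The 4-point figure needs a harsh window pattern.** This stands. Uniform windows make first doses as frequent in late April as in February, and the documents report only the day-90 share. Nor is every child first vaccinated after January 30 unobserved at day 90: one who received the second dose by April 30 has a known status.

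**The method does not create effect modification from nothing.** A reader might infer that it does so whatever the messages achieve. It does not: under a null effect the interaction is unbiased. With a real effect, the late-season risk difference has a standard error of about 4.3 points at 2,000 children, so a 4-point bias is about one standard error. Section 3.0 also requires Bonferroni bounds. If these cover the seven modifiers available for all participants and sites (an assumption), worst-case day-90 rejection falls to about 3% (2,000 children) or 6% (4,000), against 0.05/7 = 0.7% nominal. Wider bounds limit false claims but do not remove bias from the estimate.

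**Season of first dose may never enter this model alone.** Section 3.0.1 calls these candidates and warns against testing factors one by one; section 3.0.3 favours latent classes. Section 3.2 presents its model under RMST and names no horizon, so 60 and 90 days are carried over from sections 2.3.4 and 2.3.5.1. All this limits the reach of the point. But the modifier is listed, no other time-to-event model is given for it, and RMST is affected too.

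**Conclusion.** The point holds for one listed modifier in a secondary analysis under an exploratory aim. For season of first dose, covariate-independent censoring fails by design, and pooled pseudo-observations are biased when the messages have an effect. The late-season effect is usually understated. For a constant true effect of 7 to 8 points, the spurious day-90 interaction is about -0.3 to -4 points. No single value can be defended without the cut dates and the distribution of windows.

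The day-90 problem is the best supported, because 10-16% of children lack that window. At days 60 and 42 the bias depends on shares of shorter windows that the documents do not give. Direction is not guaranteed, since the sign can change if the arms converge.

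Two wider inferences are not supported. The primary as-randomized comparison and the binary subgroup analysis in section 3.1 use no pseudo-observations and are unaffected. And nothing in the documents shows that sex, age group, language or the other modifiers depend on first-dose date, so the point does not extend to them.

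**What to change.** Amend section 3.2 for the season-of-first-dose modifier:

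- State the cut dates for early, mid and late season.
- Compute pseudo-observations, for both event probability and RMST, from each season category's own Kaplan-Meier curve (arms combined), or weight for censoring given first-dose date.
- Report, by category, the share of children with windows reaching days 42, 60 and 90.
- Omit any horizon that a category's windows do not reach. If late season starts after January 30, its day-90 effect cannot be estimated without extrapolation, and a within-category curve does not rescue it.

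For other modifiers, tabulate first-dose date by modifier level, which needs no outcome data, and apply the same treatment only where they prove associated.

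The cost is a few lines of code, wider late-season intervals, and possibly no late-season day-90 contrast. If the sponsor already intends stratified or weighted pseudo-observations, saying so in section 3.2 is enough for the second item.

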## Flu2Text: A Multi-Site Study assessing an Intervention for 2nd Dose of Influenza Vaccine

### Overview of the study

This study will assess the impact of text message reminders on the receipt of the second dose of influenza vaccine and will take place in 40-50 practices over two influenza seasons.

This study includes a sample of up to 4,000 parents over the course of two flu seasons (up to approximately 40-250 parents any of 40-50 sites per influenza season). Eligible parents will have a child who received their first vaccine dose and are in need of 2 doses that season. The study will include parents who have a 6-month through 8-year-old child (or a child who is of the age that necessitates 2 doses, should age recommendations change as determined by the CDC) who received their first vaccine dose and is in need of 2 doses that season. Current recommendations require 2 doses for certain children 6 months through 8 years old.

Within each practice site, parents will be randomized to receive either:

- 1) a series of text message reminders embedded with influenza vaccine health-literacy promoting information, or
- 2) usual care

- *Season 1 (2017-2018):* usual care alone
- *Season 2 (2018-2019):* usual care plus a text message containing a link to health and parenting information from the American Academy of Pediatrics website

The primary outcome will be receipt of two doses of influenza vaccine by the end of the season (April 30). A secondary outcome will be timeliness of receipt of 2nd dose.

The study will be conducted over the 1st season (September 2017–April 2018) as an effectiveness trial and the 2nd season (July 2018–April 2019) as a replication study to validate the approach and allow refinement based on parent and practice feedback. The intervention targets the parent-child dyad.

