## **Study procedures**

### **Practice inclusion criteria:**

- Ability to recruit a minimum of 40 English or Spanish speaking parents per season
- Ability to check the office medical records and/or the city/state immunization information system of the child of the participating parent to confirm dates of first and second influenza vaccination and related visit dates in each season (and ability to provide these dates to the study team)

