### **Parent randomization**

Randomization will occur with a 1:1 allocation ratio stratified by:

- clinical site (such that each site will have a balance of intervention and usual care plus participants)
- child's age group (6-23 months vs. 2-8 years)
- parental language (English versus Spanish preference)

To ensure allocation concealment (a technique used to prevent selection bias), the CHOP/Penn statistician will prepare for each site a separate randomization list stratified by age and language, using randomly permuted blocks with varying block sizes.

If the parent is assigned to usual care, they will receive the existing influenza vaccination protocol for any given practice. This may include other forms of influenza vaccine reminders. In season 2, caregivers randomized to usual care will be sent a message upon enrollment containing a link to health and parenting information from the American Academy of Pediatrics website. If a parent is assigned to the intervention arm, we will follow the protocol under *Study Intervention: Text Messages*.

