### **3.0 AIM 3:** To assess parental and child characteristics that modify text message effectiveness

The goal for this Aim is to identify subgroups for which the intervention was either particularly effective or not effective. All subgroups should be pre-specified (see candidates below). They should also be few, owing to issues of multiple comparisons. For that reason, all confidence bounds of subgroup estimates will be adjusted so that bounds correspond to Bonferroni corrections for multiple contrasts. This aim is exploratory.

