##### **3.0.1.2 Available for all practice sites**

- appointment scheduling for the 2nd dose (walk-in; appointment)
- primary practice setting/urbanicity (urban, inner city; urban, not inner city; suburban; rural). Practice setting is self-reported and the categories align with the Periodic Survey from the American Academy of Pediatrics.

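### SAP 3.2: site-clustered bounds with normal critical values are too narrow for the two practice-level effect modifiers, and Bonferroni adjustment makes the relative error larger

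*Combined protocol and SAP*

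**What the plan says.** SAP section 3.2 estimates time-to-event effect modification on the difference scale by regressing pseudo-observations on treatment, subgroup and their interaction: "glm pseudo treat##subgroup, vce(cluster site"). It names no finite-sample correction, reference distribution or minimum number of practices per level.

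The section 3.0.1.2 list for practice sites has two candidate modifiers that are constant within a practice: scheduling of the second dose ("walk-in; appointment") and "primary practice setting/urbanicity (urban, inner city; urban, not inner city; suburban; rural"). Section 3.0 then requires that "all confidence bounds of subgroup estimates will be adjusted so that bounds correspond to Bonferroni corrections for multiple contrasts". It calls the aim exploratory.

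On scale, the Overview says that the study "will take place in 40-50 practices over two influenza seasons". Neither document says how many practices fall in each category, or how many contrasts the Bonferroni correction covers.

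**The concern.** When every child at a practice has the same modifier level, the treatment-by-level interaction compares one set of practices with another. The 40-50 practices are then not one pool of clusters. They are split among the levels, and each level's variance is estimated from its own practices alone. Four urbanicity levels leave 10 to 12.5 practices each on average (40/4 to 50/4), and an uneven split leaves some levels with fewer.

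Two errors follow. The sandwich variance is biased downward within a small level, and a correction based on the total number of practices does not repair that. Normal critical values also ignore the few degrees of freedom. The second error is relatively worse far out in the tail, which is where Bonferroni bounds are read. At stake is whether a reported difference in text-message effect between, say, rural and suburban practices carries an honest interval.

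**Working it through.** The plan states no error rate for this analysis, so there is no figure to reproduce.

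**Inputs from the documents**
- Practices: 40-50; G = 44 is used.
- Size: "This study includes a sample of up to 4,000 parents over the course of two flu seasons", so about 4,000/2/45 = 44 parents per practice per season. Practices must show "Ability to recruit a minimum of 40 English or Spanish speaking parents per season".
- Allocation: "Randomization will occur with a 1:1 allocation ratio stratified by" site, among other factors, so each practice supplies its own treatment difference.

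**Assumptions**
- Contrasts: the seven factors not taken from the questionnaire have 2+2+2+3+2+2+4 = 17 levels, hence 17 − 7 = 10 interaction contrasts. The per-contrast level is 0.05/10 = 0.005, with normal critical value 2.807.
- Software default: variance factor G/(G−1) and a normal reference.
- Equal practice sizes, no true effect modification, and the slight dependence among pseudo-observations ignored.

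**Formula.** Let d be a practice's treatment difference. For levels with g and h practices, the contrast is mean(d in A) − mean(d in B), and the clustered variance is

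V = [G/(G−1)] × [SS_A/g² + SS_B/h²],

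where SS is the sum of squares about the level mean. Its expected value divided by the true variance is [G/(G−1)] × [(g−1)/g² + (h−1)/h²] / (1/g + 1/h).

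**Exact check for even splits.** If g = h, the correctly scaled statistic is t with 2(g−1) df.
- Urbanicity 11 v 11: the effective cutoff is 2.807 × √(44/43 × 10/11) = 2.707. P(|t20| > 2.707) = 0.0136, and 0.0136/0.005 = 2.7. The right cutoff is 3.153, so bounds are 1 − 2.707/3.153 = 14% too narrow. With 40 practices (10 v 10) the multiple is 2.9; with 48 (12 v 12) it is 2.5.
- Scheduling 22 v 22: the effective cutoff is 2.807 × √(44/43 × 21/22) = 2.774. P(|t42| > 2.774) = 0.0082, or 1.6 times nominal. Bounds are 1 − 2.774/2.963 = 6% too narrow.

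**Simulation of d** (400,000 replicates per row, 10 contrasts, nominal 0.5%). The last two columns apply a per-level g/(g−1) correction with Satterthwaite df, which is what CR2 reduces to when practice sizes are equal.

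| Practices | E(V)/true | Non-coverage | × nominal | Corrected cutoff | × nominal, corrected |
|---|---|---|---|---|---|
| 4 v 20 | 0.80 | 4.8% | 9.6 | 5.30 | 0.3 |
| 6 v 18 | 0.88 | 2.4% | 4.8 | 3.74 | 0.7 |
| 8 v 14 | 0.92 | 1.7% | 3.3 | 3.30 | 0.95 |
| 11 v 11 | 0.93 | 1.4% | 2.7 | 3.15 | 1.0 |
| 15 v 29 | 0.97 | 1.0% | 1.9 | 3.04 | 1.0 |
| 22 v 22 | 0.98 | 0.8% | 1.6 | 2.96 | 1.0 |

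**Sensitivity**
- Number of contrasts: for smallest levels of 4, 6, 8 and 11 practices, the multiples are 6.4, 3.5, 2.6 and 2.2 at 5 contrasts, and 13, 6.1, 4.1 and 3.3 at 17. At an unadjusted 5% level they are 2.7, 1.9, 1.6 and 1.5.
- Reference distribution: with t on 43 df instead of the normal, the multiples at 10 contrasts are 7.9, 3.8, 2.4 and 2.0. For scheduling they are 1.3 (15 v 29) and 1.1 (22 v 22).
- Unequal practice sizes (45 practices, 10 contrasts): 5 v 18 rises from 5.8 to 7.9, and 22 v 23 from 1.5 to 1.9.
- Individual-level simulation of restricted mean time to 90 days: levels of 12, 8 and 5 practices against 20 give 2.3, 3.1 and 6.9, in line with the table.
- Patient-level modifiers draw on nearly all practices: about 1.4 to 1.7.

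**Other planned checks.** The site-level percentile bootstrap in 2.3.5.1 is written for the main RMST comparison. Extended to these contrasts it would not help: 11.1 (4 v 20), 5.4 (5 v 18), 3.2 (8 v 15) and 2.2 (22 v 23) at 10 contrasts. The permutation analysis in 3.2.2 is for latent-class subgroups. The decomposition in 3.1.2 is for binary outcomes.

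**The case against.** The case against is substantial. The aim is exploratory and section 3.2 is secondary. The SAP introduction renounces statements of statistical significance, so no rejection rule exists by which a false modifier would be declared. Section 1.0 already tells analysts to avoid small categories before looking at outcomes, which would remove the worst rows of the table. Section 3.2 describes its goal in terms of patients, and section 3.0.1 calls its list the original candidates.

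This limits the size and the consequence, but it does not remove the point. The practice factors are on the Aim 3 list, and 3.2 gives the only time-to-event interaction command without excluding them. A plan that relies on confidence bounds and promises adjusted ones should deliver roughly the stated coverage. Even an even urbanicity split, which needs no pooling, falls short by a factor of 2 to 3.

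A reader might infer more: that every practice category rests on a handful of sites, and that false modifiers appear at 3 to 13 times the nominal rate. The documents do not support this. Practices per category are not given. The figure of 13 needs a 4-practice category left unpooled and a correction counted over 17 factor levels rather than 10 contrasts. Scheduling has two levels and is well below that range unless its split is very uneven. Nor is Bonferroni the only safeguard: 3.0 asks for few, pre-specified subgroups, and 3.0.1.3 warns against testing candidates one at a time.

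**Conclusion.** Wrong as written, with limited consequences. For urbanicity and scheduling, the section 3.2 bounds are too narrow, and the relative error grows under Bonferroni adjustment. At 10 contrasts and 44 equal-sized practices, non-coverage is about 2.7 times nominal for an even urbanicity split and about 3 to 5 times with a smallest category of 6 to 8. It is 9 to 10 times only with an unpooled category of 4, and about 1.6 to 1.9 times for scheduling splits from 22/22 to 15/29. Unequal practice sizes raise these somewhat; a t reference on 43 df would lower them without curing the small-category error. In absolute terms the rate is about 1% to 5% per contrast against 0.5%.

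The direction does not depend on the unknowns, but the size does: practices per category, number of contrasts and the software's default reference are all assumptions. The finding does not reach patient-level modifiers to any important degree, or the primary analysis.

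**What to change.** For the two practice-level modifiers in section 3.2:
- Keep the child-weighted pseudo-observation model. Replace the default clustered variance with a CR2 (bias-reduced) site-clustered variance and Satterthwaite degrees of freedom.
- Take the Bonferroni quantile from that t distribution, and state the number of contrasts and the practices per category.
- Apply section 1.0 explicitly: pool urbanicity categories with fewer than about 6 practices, blind to outcome.

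An unweighted Welch interval on practice-level differences is not an interchangeable alternative. It weights practices rather than children. With 4 v 20 practices and 17 contrasts its non-coverage is about 3.2 times nominal, against about 0.2 for the Satterthwaite reference fixed by practice counts.

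The cost is SAP wording and a few lines of code. Intervals for these two factors widen: for an even urbanicity split the cutoff rises from 2.81 to 3.15. If a very small category remains, the corrected interval is conservative (cutoff 5.30 for 4 v 20), and pooling loses some detail. With unequal practice sizes, the simpler per-level correction gave about 0.5 to 1.4 times nominal at 10 contrasts; CR2 itself was not simulated in that setting.
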